6.6 Schedule of Evaluations

Table 1: Schedule of Evaluations

Visit Number	0	1	2	3	4	5
Time (Weeks [w]/Months [m])	-1m to 0	0	6w	6m	12m	18m
Window Period	-	-	±1w	±1m	±1m	±1m
Visit Type	Online + Phone	Clinic*	Phone	Clinic*	Phone	Clinic*
Remote / Electronic Informed Consent	X					
In-person Written Informed Consent		X				
SPHERE Questionnaire	X	X				
Blind MoCA	X					
Eligibility – Inclusion/Exclusion Criteria	X	X				
Medical History, Demographics & Socio-Economic Status		X				
Pregnancy Test – where required		X				
Lifestyle – Smoking, Diet, Alcohol		X		X		X
History of Health Service Use for COVID-19/Visits to Medical Professionals		X		X		X
Anthropometrics – Height & Weight		X				X
Blood Pressure, Heart Rate		X		X		X
Fasting Bloods	Haematology/Electrolytes/Renal/Liver Function – full blood count, Na, K, urea, nitrogen, creatinine, eGFR, ALT, AST, CK		X			X
	Glucose/Lipids/Inflammation – glucose, total cholesterol, LDL, HDL, triglycerides, CRP		X			X
	Neurodegenerative Biomarkers – 220 participants		X			X
Cognitive Assessments – SDMT, RAVLT-D, OTMT-A, OTMT-B, D-KEF-CWIT, SF		X		X		X
Health Assessments – PHQ-9, GAD-7, PSQI, EQ-5D-5L		X		X		X
Actigraphy plus Sleep Diary – 7-day Capture		X		X		X
Brain MRI – 220 participants		X				X
Dispense Study Medication – treatment arm only		X		X	X	
Study Medication Adherence & Accountability – treatment arm only			X	X	X	X
Concomitant Medications		X	X	X	X	X
SAEs/AESIs			X	X	X	X

*For participants who cannot attend the clinic, efforts will be made for visit assessments to be conducted remotely via tele-/videoconference.

ALT – Alanine Aminotransferase

AST – Aspartate Aminotransferase

CK – Creatine Kinase

CRP – C-Reactive Protein

D-KEF-CWIT – Delis-Kaplan Executive Functioning System “Stroop” Colour-Word Interference Test

GAD-7 – Generalised Anxiety Disorder-7

HDL – High-Density Lipoprotein

LDL – Low-Density Lipoprotein

MoCA – Montreal Cognitive Assessment

MRI – Magnetic Resonance Imaging

PSQI – Pittsburgh Sleep Quality Index

RAVLT-D – Rey Auditory Verbal Learning Test – Delayed Recall

SDMT – Symbol Digit Modalities Test

SF – Semantic Fluency

SPHERE – Somatic and Psychological Health Report

eGFR – estimated Glomerular Filtration Rate
EQ-5D-5L – EuroQoL 5-Dimensional 5- Level Questionnaire

OTMT – Oral Trail Making Tests A & B
PHQ-9 – Patient Health Questionnaire-9

6.7 Visit Summary

In-person visits will be supplemented with telephone interviews to check on a participant's ongoing health status, adherence to study medication, and any AEs/SAEs, as well as to provide support and appointment reminders. If participants are unable to attend in-person visits, Zoom based (or telephone) interviews will be undertaken to assess the various health measures, where possible.

6.7.1 Preliminary Screening

Preliminary screening will be conducted via telephone or via an online portal to assess key inclusion and exclusion criteria that can be assessed remotely.

6.7.2 Visit 1 – Screening, Baseline & Randomisation

After preliminary screening, potentially eligible participants who have provided remote consent will be invited to attend a morning appointment at a research clinic in a fasting state to complete the screening process and, if eligible, baseline assessments. (If required e.g. if results of blood tests are not available on the same day, the visit can be split across 2 days). If participants are unable to attend these clinics and are otherwise eligible and willing to participate in the study, efforts will be made to conduct all assessments remotely.

At the screening visit, the following assessments will take place:

- Informed consent
- Eligibility assessment
- Review of participant's demographics, socio-economic status and lifestyle – smoking, diet and alcohol intake
- Review of participant's medical history including health service use
- Measurement of height and weight
- BP and HR
- Blood sample – following an overnight fast
 - Haematology/electrolytes/renal/liver function – full blood count, sodium, potassium, urea, nitrogen, creatinine, eGFR, ALT, AST, CK
 - Glucose/lipids/inflammation – glucose, total cholesterol, low-density lipoprotein (LDL), high-density lipoprotein (HDL), triglycerides, CRP
 - *Neurodegenerative biomarkers (sub-study group: 220 participants)*
- Cognitive Assessments
 - Symbol Digit Modalities Test (SDMT), Rey Auditory Verbal Learning Test – Delayed Recall (RAVLT-D), Oral Trail Making Test (OTMT) (A & B), Delis-Kaplan Executive Functioning System “Stroop” Colour-Word Interference Test (D-KEF-CWIT), Semantic Fluency (SF)
 - Cognitive assessments will be undertaken in a separate session within 7-10 days of the clinical assessment by research personnel with skills in cognitive measures. Personnel conducting cognitive assessments will be kept blind to the participants' treatment allocation. Treatment allocation (randomisation) will be undertaken by the research coordinator using the study database following review of the participant's routine blood tests.
- Health Assessments
 - Patient health questionnaire 9 (PHQ-9), generalised anxiety disorder 7 (GAD-7), Pittsburgh sleep quality index (PSQI), EuroQoL 5-Dimensional 5-Level Questionnaire (EQ-5D-5L)
- Provision of actigraphy watch and sleep diary

- Actigraphy watches and a sleep diary will be mailed to all participants for recording of their physical activity and sleep over a 7-day period in the next 2 weeks, and then returned by courier to a central office for downloading of data.
- *Brain MRI (sub-study group: 220 participants)*
- Randomisation – if eligible
 - After confirmation of eligibility, participants are randomised to receive standard care or study medication (atorvastatin 40mg) according a stratification scheme that involves (see Section 11.2) country, time since the acute COVID-19 illness, age, current anosmia, and participation in the MRI/biomarker substudy .
 - Participants will only be informed of their treatment allocation once they have completed all baseline assessments, in order to reduce the risk of differential withdrawal between the two arms.
- Dispense study medication – treatment arm only
 - Study medication will be dispensed in person or via courier in each country; if the latter, an SMS message will be sent by the participant to the regional research office to confirm receipt of study medication. If no message is received, the office will contact the participant by telephone for confirmation.
- Record of concomitant medications

Visit 1 will take approximately 3-4 hours.

All women of child-bearing potential must have a confirmed menstrual period and a negative highly sensitive pregnancy test 7 days or fewer before starting run-in medication and must use a highly effective method of contraception throughout their participation in the study. Highly effective contraceptive methods include hormonal contraception (oral, intravaginal, transdermal, injectable, implantable) or intrauterine device. These methods are not required in the case of bilateral tubal occlusion, vasectomised partner or true sexual abstinence (i.e. within line of the person's preferred and usual lifestyle).

A subset of participants (n=220) will be invited to participate in a sub-study involving:

- the collection and storage of blood for future neurodegenerative biomarker studies, and
- Brain MRI scanning (45 mins).

These additional assessments will be undertaken either the same day or within the next 7-10 days of the baseline clinical assessment, according to booking availability. See Section 6.10 for further information.

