6.1 Study Design

STRONGER is an international, investigator-initiated and conducted, multi-centre, prospective, randomised, open-blinded end-point (PROBE) study, with fixed time point for outcome assessments. Participants randomised to the intervention group will receive 40mg atorvastatin for up to 18 months.

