7.1 Study Treatment

Participants who meet the eligibility criteria will be randomised to receive standard care or 6-monthly supplies of atorvastatin 40mg on top of standard care for a period of 18 months.

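### The 7-day pregnancy-test limit is timed from a run-in that the trial does not have; read as the first atorvastatin dose, a first-session test can be 1 to 3 days too old

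*Protocol*

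**What the plan says.** Protocol section 6.7.2 (Visit 1) requires women of child-bearing potential to have a confirmed menstrual period, a negative highly sensitive pregnancy test "7 days or fewer before starting run-in medication", and highly effective contraception throughout.

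The design and treatment sections describe no run-in. Section 6.1: "Participants randomised to the intervention group will receive 40mg atorvastatin for up to 18 months". Section 7.1: eligible participants "will be randomised to receive standard care or 6-monthly supplies of atorvastatin 40mg on top of standard care".

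Table 1 in section 6.6 has one row headed "Pregnancy Test", marked at Visit 1 only and applied where required. It names no session within Visit 1 and no repeat. Nothing is dispensed at Visit 0; drug is first dispensed at Visit 1, to the treatment arm only.

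Section 6.7.2 spreads the baseline work over several days:

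- Cognitive testing, for all participants: "Cognitive assessments will be undertaken in a separate session within 7-10 days of the clinical assessment by research personnel".
- MRI and biomarker sampling, for the sub-study: "These additional assessments will be undertaken either the same day or within the next 7-10 days of the baseline clinical assessment".
- Disclosure of allocation: "Participants will only be informed of their treatment allocation once they have completed all baseline assessments".

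Drug is then handed over in person or sent by courier. The courier time is not stated.

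**The concern.** The protocol sets a numeric safety limit and ties it to an event that the trial does not contain. A site must therefore decide what was meant. The candidates (first dose, randomisation, the Visit 1 date) give different latest acceptable dates for the test.

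The natural reading is the first atorvastatin dose, because there is only one study drug. On that reading the limit has a clear purpose, but nothing in the visit plan leads a site to meet it. The single scheduled test can be done at the start of Visit 1, while the earliest point at which a participant can learn that she is to take the drug may be more than a week later.

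What is at stake is exposure to atorvastatin in an unrecognised early pregnancy. Exclusion criterion 7 covers contraception, breastfeeding and planning a pregnancy, but does not name current pregnancy. The sentence in section 6.7.2 is thus the only express demand for a negative result. The step described just before allocation mentions a different check: "Treatment allocation (randomisation) will be undertaken by the research coordinator using the study database following review of the" participant's routine blood tests. For women in the standard-care arm a first-dose anchor has no meaning, so when their test must be done is also left open.

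**Working it through.** No power, sample-size or alpha figure is involved. The check is a comparison of texts followed by a day count.

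**Step 1: does the anchor exist?**

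| Place in the protocol | Medication before randomisation? |
|---|---|
| 6.1 Study Design | No; atorvastatin goes to those randomised to it |
| 6.6 Table 1, Visit 0 | No; online and telephone screening, nothing dispensed |
| 6.6 Table 1, Visit 1 | First dispensing, treatment arm only |
| 6.7.1 to 6.7.6 visit summaries | No run-in step; the term appears only in the pregnancy-test sentence of 6.7.2 |
| 7.1 Study Treatment | No; direct randomisation to atorvastatin or standard care |

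The anchor does not exist.

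**Step 2: test age on the first-dose reading.**

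Inputs:

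- The test is done at the first Visit 1 session, called day 0. This is an assumption, since the protocol does not fix the session.
- The last baseline session is on day *s*, from 0 to 10. The upper end comes from the 7-10 day windows for cognition and MRI in section 6.7.2, read as allowing up to 10 days.
- Allocation is disclosed no earlier than day *s* (6.7.2; section 7.2 says the same).
- Delivery time is *D* days. It is 0 for in-person handover on the day of disclosure; for courier the protocol gives no figure.
- The limit is 7 days.

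Formulas: earliest test age at first dose = *s* + *D*; days over = max(0, *s* + *D* − 7).

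Results with *D* = 0:

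| Last baseline session (day *s*) | Test age (days) | Days over the limit |
|---|---|---|
| 0 to 7 | 0 to 7 | 0 |
| 8 | 8 | 1 |
| 9 | 9 | 2 |
| 10 | 10 | 10 − 7 = 3 |

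**Step 3: sensitivity to the assumptions.**

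- *Courier time.* If *D* is assumed to be 1 to 5 days, a last session on day 10 gives a test age of 11 to 15 days, which is 4 to 8 over. That range is illustrative.
- *Actigraphy.* The baseline recording runs for 7 days within the following 2 weeks. It is not counted here as a baseline assessment. If it were, disclosure could wait until about day 14, which is 14 − 7 = 7 over.
- *Test placed later.* A test on the day of disclosure has age *D* at the first dose, so it is within the limit whenever *D* is 7 or less.

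**The case against.** The strongest reply is that this is one stray term. The trial has a single study drug, so the phrase can only sensibly mean its first supply. There are dates to compare with the test: section 14.5 requires a dispensing log, and section 6.7.2 has courier receipt confirmed by text message or telephone. This stands. A reader might infer that sites and monitors cannot check the limit at all; the documents do not support that.

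The second reply is that the overrun is not something the protocol directs. It needs three things together: a test at the first session, a last session on day 8, 9 or 10 (or a courier delay), and no repeat despite a sentence that makes a test within 7 days mandatory. This also stands. A reader might infer an unavoidable breach, or a direct contradiction between the limit and Table 1. Neither follows, because Table 1 leaves the session open and a site may test late or test again. Nor do the three late days give a probability, since nothing is known of how sessions will be spread over the window.

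Third, a reader might infer that women can be randomised with no pregnancy check. That goes too far. Section 6.7.2 has randomisation follow confirmation of eligibility, Table 1 puts the eligibility check and the pregnancy test in the same visit, and the requirement covers all women of child-bearing potential. The timing relative to randomisation is unstated; the requirement itself is not absent.

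Fourth, other protections apply: the confirmed menstrual period, contraception throughout, exclusions 4 and 9, and the instruction in section 8 to consult the Product Information. They lower the stakes, but none of them sets a date for the test.

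What survives is a wrong anchor in an operative safety rule, and a visit plan with no prompt for a repeat.

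**Conclusion.** The point holds as a minor one. The 7-day limit is tied to an event that does not occur. Read as the first atorvastatin dose, it can be applied, but the schedule does not help a site to keep it.

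The possible excess is 1 to 3 days before courier time. This rests on a first-session test, a last baseline session on days 8 to 10, disclosure only once baseline is complete, and no repeat test. With a last session by day 7 and drug handed over that day, or with a later or repeated test, there is no excess.

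Confidence is high on the missing run-in, which is a matter of text. The overrun is a possible gap whose frequency cannot be judged from the protocol. There is no effect on the sample size or the primary analysis.

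**What to change.** Three wording changes:

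1. In section 6.7.2, replace the reference to a run-in with *the first dose of study medication (atorvastatin arm)*.
2. In section 6.7.2, state that all women of child-bearing potential, in both arms, need a negative highly sensitive test before randomisation.
3. In section 6.7.2, and as a footnote to the pregnancy-test row of Table 1, add: *Atorvastatin arm: repeat the test if it will be more than 7 days old at the first dose; the first dose is taken only after a negative result.*

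The first change alone cures the textual error. The second gives the standard-care arm a usable date, and the third makes the visit plan carry the limit.

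The cost is an occasional repeat test and a short delay to the first dose. Rarely, a randomised woman will have a positive repeat test and not start the drug; under the intention-to-treat principle in section 11.3 she stays in the analysis.

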6.7.3 Visit 2 – 6 Weeks (\pm 1 Week) – Telephone

The following will be assessed at the 6-week phone call:

- Review of any SAE/AESIs since last visit
- Adherence to study medication (participant-reported) – treatment arm only
- Changes to concomitant medications

6.7.4 Visit 3 – 6 Months (\pm 1 Month) – Clinic

The following will be assessed at the 6-month clinic visit:

- Review of any SAE/AESIs since last visit
- BP and HR
- Adherence to study medication (pill count) – treatment arm only
- Changes to concomitant medications
- Review health service use and lifestyle questions
- Cognitive Assessments
 - SDMT, RAVLT-D, OTMT-A, OTMT-B, D-KEF-CWIT, SF
 - Cognitive assessments will be undertaken in a separate session within 7-10 days of the clinical assessment by a separate blinded research person with skills in cognitive measures.
- Health Assessments
 - PHQ-9, GAD-7, PSQI, EQ-5D-5L
- Download of actigraphy watch data
- Collect sleep diary
- Fasting blood tests – routine measures of haematology, biochemistry, renal function, lipids, glucose, and inflammatory markers
- Dispense of study medication (to be sent via courier/mail) – treatment arm only

This visit will take approximately 2-3 hours.

6.7.5 Visit 4 – 12 Months (\pm 1 Month) – Telephone

The following will be assessed at the 12-month phone visit:

- Review of any SAE/AESIs since last visit
- Adherence to study medication (participant-reported) – treatment arm only
- Changes to concomitant medications
- Dispense of study medication (to be sent via courier/mail) – treatment arm only

6.7.6 Visit 5 – End of Study 18 Months (\pm 1 Month) – Clinic

The following will be assessed at the 18-month End of Study clinic visit:

- Review of any SAE/AESIs since last visit
- Measurement of height and weight
- BP and HR
- Adherence to study medication (pill count) – treatment arm only
- Changes to concomitant medications
- Review medical history and lifestyle questions
- Blood sample – following an overnight fast
 - Haematology/electrolytes/renal/liver function – full blood count, Na, K, urea, nitrogen, creatinine, eGFR, alanine aminotransferase (ALT), aspartate aminotransferase (AST), CK
 - Glucose/lipids/inflammation – glucose, total cholesterol, low-density lipoprotein (LDL), high-density lipoprotein (HDL), triglycerides, CRP
 - Neurodegenerative biomarkers (220 participants)

- Cognitive Assessments
 - SDMT, RAVLT-D, TMT-A, OTMT-B, D-KEF-CWIT, SF
 - Cognitive assessments may be undertaken in a separate session within 7-10 days of the clinical assessment and/or by a separate research person with skills in cognitive measures who remains blind to the treatment allocation.
- Health Assessments
 - PHQ-9, GAD-7, PSQI, EQ-5D-5L
- Download of actigraphy watch data
- Collect sleep diary
- Brain MRI with biomarkers (subset of 220 participants)

This visit will take approximately 3-4 hours.

6.8 Assessment Details

6.8.1 Screening Questionnaire 'SPHERE'

The SPHERE questionnaire will be administered at screening to assess for long COVID symptoms. It is a 34-item self-report questionnaire that was developed to assess symptoms of mental distress and persistent fatigue, with questions selected from other common scales. Participants respond to each of the items, choosing from one of three fixed options ('sometimes/never', 'often', and 'most of the time', which are coded 0, 1, and 2, for calculating a sum score) to describe the frequency of their symptoms over the 'past few weeks'.

This study will use the original 34-item scale to identify any positive response to the three arms of SPHERE: anxiety-depression, somatic distress and persistent fatigue. There is no score threshold for inclusion.

People with anosmia will be included as this is a heterogeneous condition with uncertain relationship to olfactory neuronal circuitry and encephalitis, where neuroimaging and long-term follow-up are required.³⁰

6.8.2 Blind MoCA

The Blind MoCA will be administered at screening via telephone to assess for any significant cognitive impairment. The MoCA is a brief screening test for cognitive impairments that has been validated as a remote alternative to the full MoCA that can be administered over the telephone. It is scored out of 22 with a cut-off of N <19 indicating significant cognitive impairment for which subjects will be excluded from participating in the study.

6.8.3 Cognitive Assessments

Cognitive assessments will be administered between 9:30am and 12:30pm. Completion of all assessments will take approximately 40 mins.

Name	Format	Purpose	Assessment	Scoring	Normative Data	Test-Retest Reliability
SDMT	Oral	Assesses frontal lobe executive processing.	Requires participants to match numbers to symbols according to a key, containing 9 abstract symbols each paired with a number. Participants verbalise the correct number.	The number of correct symbols within the allowed time, usually 90 seconds ²⁸	There are Australian normative data available for the oral SDMT. ²⁹	The oral SDMT demonstrates excellent test-retest reliability (an intraclass correlation coefficient of 0.89) and only has a small learning effect (Cohen's $d = 0.26$) within a 1-week interval. ³⁰
RAVLT-D	Oral No difference in videoconferencing and face-to-face RAVLT-D have been reported. ³¹	Assesses memory and learning. ³²	Requires participants to learn a 15-item word list over 5 learning trials, followed by a distractor list, and short and long-delayed recall.	Max score = 15	Australian normative data is available in Carstairs, Shores and Myers (2012). ³³	Test-retest reliability of the RAVLT has been reported, with the most reliable measures being the total number of words learned over the learning trials ($r = 0.77$), and performance on the retention trial of the learning list following the presentation and performance of the distractor list ($r = 0.70$). ³²
OTMT-A & B	Oral	Provides information on visual search, scanning, speed of processing, mental flexibility, and executive functions. The OTMT is a sensitive measure of early cognitive decline in relation to vascular-related factors. ^{34, 35}	Part A – participant is asked to count from 1 to 25 as quickly as possible. In Part B – participant is asked to progressively alternate between counting numbers up to 13 and reciting letters of the alphabet up to L as quickly as possible.	Scores relate to time for completion. The primary performance metric is the time in seconds required to complete each of the two parts of the test.	Age-based norms (for ages 20 to 90) are available in Mrazik, Millis, and Drane (2010). ³⁶	The OTMT-B demonstrated moderate test-retest reliability. Scores showed significant agreement (intraclass correlation = .62, $p < .0001$), a significant correlation (Pearson $r = .62$, $p < .0001$), and similar mean scores ($M = 41.85$, $SD = 32.55$; $M = 43.40$, $SD = 30.18$) across administrations. ³⁷

Name	Format	Purpose	Assessment	Scoring	Normative Data	Test-Retest Reliability
D-KEF-CWIT	Oral	
A battery of neuropsychological tests designed to measure executive functions in children and adults, ages 8–89.
 
It is based on the Boston process approach³⁸ which stipulates that there is a primary function that each test is designed to measure, but also that component functions contribute to performance on a particular test.³⁹
	Four parts: colour naming, word reading, inhibition, and inhibition/switching. ³⁹	Performance is measured by completion time on each of the four trials. In addition, colour naming and word reading times may be summed for a composite score representing component functions. Three contrast scores (inhibition vs. colour naming, inhibition/switching vs. combined colour naming and word reading, and inhibition/switching vs. inhibition) may be calculated to determine whether there is a disproportionate impairment in a higher-level function than the component function(s).	Australian normative data not available.	The majority of contrast measures demonstrated low reliabilities: of the 51 reliability coefficients calculated in the present study, none exceeded 0.7 and hence all failed to meet any of the criteria for acceptable reliability proposed by various experts in psychological measurement. ⁴⁰
SF	Category fluency to animals is valid and reliably assessed via videoconference compared to assessed via traditional face-to-face assessment. ⁴¹	Assesses language processing.	Requires the generation of as many 'animal names' in 1-minute.	Counting the number of correct unique semantic category items produced.	Normative data is available in Chami et al. (2018) ⁴²	Category fluency to animals demonstrated intraclass correlation coefficient = 0.98. ⁴³

